#### 5.2.4 Professional Representative consent (England only)

**In sites recruiting in England:** If the patient does not have capacity, and there is not a Personal representative available, consent from a Professional Representative will be sought. The definition is as follows:

Professional legal representative i.e. a doctor responsible for the medical treatment of the adult if they are independent of the study, or a person nominated by the healthcare provider

If there is not a Personal Representative immediately available (within 30 minutes), a Professional Representative will be approached to determine if it is appropriate for the patient to be entered into the trial so that treatment could be commenced within one hour. A Personal Representative should be approached for consent to continue as soon as they are available, and it is feasible to do so. If the Personal Representative is unable to visit the hospital in person, the consent form will be sent to them by email or post. The Personal Representative will be asked to return the signed consent form if they wish to remain in the trial or contact the study team if they wish to be withdrawn. If the patient does not return the signed consent form but does not ask to be withdrawn from the trial, the Professional Representative consent will remain valid.

#### 5.2.5 Deferred Consent (England only)

Patients who have “life threatening features” and who lack temporary capacity due to their current illness can be recruited to the trial using deferred consent if there is no Personal/Professional Representative to give consent on their behalf within 30 minutes so that treatment can be commenced within one hour. The decision to defer consent should be made by a senior doctor, i.e. ST4 (or above) or consultant, who has appropriate trial training and this should be clearly documented.

The patient would be enrolled into the trial and receive their allocated treatment. Consent would be sought as soon as possible from a Personal Representative (or a Professional Representative if they are available sooner). If a Personal/Professional Representative

declines to give consent for continuation at this stage, their wishes will be respected and the withdrawal process in section 5.4 will be followed.

[figure not shown]
[figure not shown]
### 5.2.6 When the participant regains capacity

When the participant regains capacity to consent (as assessed by a clinician), they will be given a Recovered Capacity PIS which will explain what has happened to them so far and seek written consent for continued participation in the trial. This will be done as soon as it is feasibly possible. If the participant is happy to continue, they will be asked to provide written consent. The Investigator or delegated member of the trial team and the participant will sign and date the Consent Form to confirm that consent has been obtained. The original consent form will be filed in the Investigator Site File (ISF), the participant will receive a copy of this document and a copy filed in the participant's medical notes.

In the event that a patient is not able to be approached for consent to remain in the trial prior to hospital discharge, the local research team will seek written consent by sending a PIS and consent form by post. The patient will be asked to return the signed consent form if they wish to remain in the trial or contact the study team if they wish to be withdrawn. If there is no response, one further reminder can be sent after one month by post. If the participant does not return the signed consent form but does not ask to be withdrawn from the trial, the Professional Representative consent will remain valid and the participant will remain in the trial.

If the participant is not happy to continue, the withdrawal process in section 5.4 will be followed.

For any participant who was included but does not regain full capacity, consent from the Personal Representative will stand, or from the Professional Representative where there is no Personal Representative. Where no consent is given by any legal representative, i.e. deferred consent is used and no subsequent consent obtained, or a participant dies before any consent obtained the patient data collected would be destroyed. Patients with permanent incapacity will not be recruited and this is an exclusion criterion.

## 5.3 WITNESSED METHODS OF OBTAINING SIGNATURES

Consent will normally be recorded in writing, dated and signed or otherwise marked by the participant or their legal representative. In most instances this will take the form of a face-to-face consent process with a wet ink signature.

If face-to-face consent is not possible or feasible, verbal consent over the phone or video-call will be utilised, this will be witnessed and recorded in writing. If a verbal witnessed consent procedure is utilised we will also attempt to obtain a written signature from the participant or their legal representative by posting the consent form to them for signature and return as described previously.

## 5.4 WITHDRAWAL OF STUDY PARTICIPANTS

Participants are free to withdraw from the study at any point or a participant can be withdrawn by the Investigator, or their Personal/Professional Representative (where appropriate). If withdrawal occurs, the primary reason for withdrawal will be documented in the participant's case report form, if possible. They will have the option of withdrawal from:

- i) Further blood sampling but consent to continuation of data collection from routine medical records and use of sub-study data collected up to that point
- ii) All aspects of the trial but continued use of sub-study data collected up to that point.

To safeguard rights, the minimum personal information possible will be collected.

If a participant withdraws from the main study (ABC Sepsis) they will be asked whether or not they wish to be withdrawn from the sub-study.

# 6 STUDY ASSESSMENTS

## 6.1 STUDY ASSESSMENTS

During this trial the following assessments will be completed:

Assessment	Screening	Baseline	12 ( $\pm 4$ ) hours*	24 ( $\pm 6$ ) hours*	30 days	90 days
Consent	X					
Eligibility	X					
Demographics, Medical History		X				
Blood samples (EDTA and PAXgene tubes)		X	X	X		
Vital signs		X	X	X		
Mortality #					X	X
Length of stay, Ward/HDU/ICU stay #					X	X
Adverse events #		X	X	X		

\*after enrolment. #This data will be collected on the ABC sepsis CRF and shared with the MIS-ABC trial

## 6.2 BLOOD SAMPLING

Participants in the MIS-ABC trial will have samples taken at three points:

- Baseline (0 hrs): this sample will be taken at the point of enrolment into the sub-study, with the aim of characterising the inflammatory response to sepsis before, or at, the point of administration of the trial intervention.
- Second sample (12 ±4 hrs) after enrolment
- Last sample (24 ± 6 hrs) after enrolment

In each case, two samples will be taken sequentially, from the same point of access. In order to minimise burden to the participants, the study team will work with the clinical team to identify opportunities to take blood simultaneously with routine sampling, as well as identifying sampling options which use existing points of access. Examples of this include:

- Taking research samples at the same time that venepuncture is being performed for routine clinical samples (e.g. taking the research samples with the routine samples from the same 'butterfly needle')
- Taking research samples at the same time that a new, or re-sited, point of vascular access is inserted (e.g. taking the research samples when a new peripheral cannula is inserted)
- Taking research samples from an existing port of vascular access which allows sampling (e.g. taking research samples from an arterial line, a central line or a PICC).

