#### 2.1.2 Secondary Objectives

1. To understand the inflammatory response in patients with community acquired infection/sepsis by the analysis of a panel of cytokines.
2. To evaluate whether the early inflammatory response to infection/sepsis at the time of presentation to secondary care predicts clinically important outcomes.
3. To investigate whether transcriptomic analysis can provide an explanation for varying physiological response to fluid therapy and clinical outcomes in infection/sepsis.

[figure not shown]

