## 3 STUDY DESIGN

This is a prospective observational study enrolling patients randomised to the ABC Sepsis study. Centres for this trial will be selected from UK NHS hospitals who are recruiting to the main ABC Sepsis study. Participants will be recruited as soon as possible, and up to 12 hours after presentation to the Emergency Department, Surgical Assessment Unit or Medical Admissions Unit.

The treatment phase of the main study spans 6 hours following randomisation, with the follow up period extending to 90 days. This sub-study requires three blood samples: immediately after enrolment, at approximately 12 and 24 hours thereafter. The follow up period similarly extends to 90 days, using routine data from the medical records for follow up.

Study diagram depicting MIS-ABC Sepsis trial in the context of the main ABC Sepsis feasibility trial.

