## 7.1 SOURCE DATA DOCUMENTATION

Data will be collected from consent until final follow up visit.

Source data will either be study specific or routine clinical data. Study specific source data, including consent forms, eligibility criteria forms, and sampling details (e.g. timing of samples) will be recorded on the relevant pseudonymised source study data worksheets distributed to participating sites.

Clinical data, including physiological observations and blood samples taken as part of routine care, will be recorded according to local practice and transcribed onto the study data worksheets as agreed by site-specific source document plans.

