## 7.2 CASE REPORT FORMS

Paper CRFs (study data worksheets) will be completed as the participant progresses through the study and then entered into a database on a trial database on a secure NHS computer. Scanned images of the worksheets may also be sent to the trial management team for quality assurance purposes.

Processing of samples will be recorded on 'processing logs', paper sheets which will record the time and date of processing, number of samples and person processing them. They will be shared with the trial management team in a similar manner to the study data worksheets.

Clinical outcome data will be collected as part of the ABC Sepsis study from NHS records and will include comorbidities; vital signs, routine blood results including baseline kidney function, liver function and albumin; relevant investigations or interventions including surgery, vasopressor use, renal replacement therapy, invasive ventilation, chest x-rays, prescriptions; time of start of ABC Sepsis IMP; length of stay including critical care, repeat hospitalisations, adverse events and decisions regarding treatment escalation planning and resuscitation. Detail will also be collected on the trial intervention including timing and volume of fluids. Length of stay and repeat hospitalisation will be recorded as part of follow up. These data will be shared with this sub-study in line with the ABC Sepsis data management plan for sharing and reuse.

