## 9.2 PROPOSED ANALYSES

This project is primarily an exploratory analysis. We will report results by group as defined by the treatment arm into which they are enrolled, as well as by key outcomes (e.g. mortality at 30 days, admission to ICU). No interim analyses will be conducted.

Analysis will be conducted, across treatment arms, of individual biomarkers as part of our cytokine panel, whether at individual timepoints or in terms of the change, and rate of change, from baseline results. It will also incorporate analysis of grouped variables (e.g. 'pro-inflammatory cytokines' versus 'anti-inflammatory cytokines', or those known to be representative of specific pathophysiological damage like endothelial damage), again at individual timepoints or in terms of the change, and rate of change, from baseline. Further grouping may be taken, depending on the spread of our physiological data, to determine differences between 'responders' to fluid challenge versus 'non-responders' in either treatment arm.

Taken as a whole, we will assess the accuracy of these biomarkers as predictors of our key clinical endpoints, with consideration of sensitivity, specificity and positive or negative predictive values. Receiver operator characteristic analysis will be explored for biomarkers with significant biological plausibility or which show promise in the preceding analysis. Transcriptomic data from RNA-seq will be interrogated to determine changes in RNA abundance at the gene level between sample points and by treatment arm, as well as at the transcript isoform level.

Using the inclusion criteria mentioned before, it is plausible that we will include patients who ultimately are diagnosed with a pathology other than sepsis as a reason for their presentation to hospital. The inclusion of the results of such patients in the described analyses will be decided on discussion with the broader study team in the context of the frequency of this occurrence as well as the potential bias this might incur with the specific analysis.

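### Objective 2 treats the first sample as the response at presentation, but it is taken at enrolment, up to 12 h later, and presentation time is not among the listed data

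*Protocol*

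**What the plan says.** **What the first sample is meant to be.** Protocol Section 2.1.2, objective 2, asks whether the early inflammatory response "at the time of presentation to secondary care predicts clinically important outcomes". The hypothesis at the end of Section 1.1 refers to cytokine levels at ED admission. Section 1.2 places the first of the serial samples at hospital presentation.

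**When it is taken.** Section 6.2 fixes the baseline sample at enrolment into the sub-study. Section 3 allows recruitment "up to 12 hours after presentation to the Emergency Department, Surgical Assessment Unit or Medical Admissions Unit", and Section 5.1 gives the same limit for approaching patients.

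**When the later samples are taken.** Section 6.2 gives "Second sample (12 ±4 hrs) after enrolment" and "Last sample (24 ± 6 hrs) after enrolment". Staff are to "identify opportunities to take blood simultaneously with routine sampling", or to use new or existing vascular access. Section 11.2.2 explains that the leeway is there to spare patients extra venepuncture.

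**How time enters the analysis.** Section 9.2 plans to report by arm and by key outcomes such as 30-day mortality and ICU admission. Biomarkers are to be examined "whether at individual timepoints or in terms of the change, and rate of change, from baseline results". It does not say whether time means recorded or scheduled hours, and it does not mention time since presentation.

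**What times are recorded.** Section 7.1 lists "sampling details (e.g. timing of samples" within the study-specific source data. Section 7.2 lists "time of start of ABC Sepsis IMP" among the items shared from the main trial. Sections 7, 7.1 and 7.2 do not name time of presentation.

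**The concern.** The stated objective and the sampling schedule run on different clocks. One participant's baseline may be drawn on arrival and another's 12 h into the hospital stay, yet objective 2 and the hypothesis describe both as the response at presentation.

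This matters most for comparisons by outcome. Those groups are not randomised, and the moment of enrolment and the moment of each later draw may both relate to how ill the patient is and how closely the patient is watched. Section 6.2 ties later draws to routine bloods and existing lines, and patients on their way to ICU may offer different opportunities from stable ones. A marker could then look prognostic, or fail to, partly because of when blood was taken.

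The study has particular reason to be exact here. Section 9.1 sets it apart from earlier work that sampled over days to weeks, so timing on the scale of hours is much of what it adds.

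**Working it through.** The protocol gives no interval between samples and no time since presentation, so it has no figure of its own to reproduce. The check is interval arithmetic on its stated windows.

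**Inputs**
- Enrolment: 0 to 12 h after presentation (Sections 3 and 5.1).
- Sample 1: at enrolment (Section 6.2).
- Sample 2: 12 − 4 = 8 to 12 + 4 = 16 h after enrolment (Sections 6.1 and 6.2).
- Sample 3: 24 − 6 = 18 to 24 + 6 = 30 h after enrolment (Sections 6.1 and 6.2).

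**Time since presentation** (enrolment delay plus sample window)

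| Sample | Earliest | Latest |
|---|---|---|
| 1 | 0 h | 12 h |
| 2 | 0 + 8 = 8 h | 12 + 16 = 28 h |
| 3 | 0 + 18 = 18 h | 12 + 30 = 42 h |

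Between different participants, sample 1 overlaps sample 2 at 8 to 12 h after presentation, and sample 2 overlaps sample 3 at 18 to 28 h. Within a participant, the interval from baseline is 8 to 16 h for sample 2 and 18 to 30 h for sample 3. These two do not overlap.

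**Typical rather than extreme spread.** The protocol gives no distribution of times. If times were uniform and independent within each window (an assumption), the standard deviations of time since presentation would be:
- sample 1: 12/√12 = 3.5 h
- sample 2: √(12²/12 + 8²/12) = 4.2 h
- sample 3: √(12²/12 + 12²/12) = 4.9 h

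Earlier enrolment in practice would shrink these.

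**What such a spread could do to a marker.** The documents give no cytokine kinetics. Assume, for illustration only, that a level falls steadily with half-life h. Two otherwise identical patients drawn d hours apart then differ by a factor of 2^(d/h).

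| Assumed half-life | Baseline samples 12 h apart | Sample 2 drawn at 8 h v 16 h |
|---|---|---|
| 6 h | 2^(12/6) = 4.0 | 2^(8/6) = 2.5 |
| 12 h | 2^(12/12) = 2.0 | 2^(8/12) = 1.6 |
| 24 h | 2^(12/24) = 1.4 | 2^(8/24) = 1.3 |

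These are differences between the ends of the windows, not expected biases. Bias in an outcome comparison also requires draw time to differ between the outcome groups, and the protocol gives no information on that.

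**Can the recorded data deal with it?** For samples 2 and 3 relative to baseline, yes: draw times are recorded. For placing any sample relative to presentation, the missing item is time of presentation. Sites need it to apply the 12 h limit, so it should already exist locally.

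**The case against.** **Choice of time scale and covariates belongs in an analysis plan.** Largely true. The absence of that detail from Section 9.2 is not an error, and an analysis plan that is not shown may supply it. But an analysis plan does not change what objective 2 claims to measure, and it cannot adjust for a time that never reaches the dataset.

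**A reader might infer that samples will be analysed at nominal 0, 12 and 24 h.** The protocol does not say so. It plans rates of change and records actual draw times. If change to sample 2 were divided by a nominal 12 h, the rate would be scaled by 8/12 = 0.67 to 16/12 = 1.33, but no such rule is stated.

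**A reader might also point to the gap between samples 2 and 3,** which can be 18 − 16 = 2 h to 30 − 8 = 22 h. The arithmetic is right, but Section 9.2 measures cytokine change from baseline, not from sample 2 to sample 3. Only the RNA analysis is described between sample points, and Section 6.4 says its funding is not yet secured.

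**Twelve hours is a ceiling.** Section 3 asks for prompt recruitment, and the consent sections speak of trial treatment starting within one hour. This makes long delays less typical. It does not withdraw the 12 h allowance.

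**The windows are a deliberate trade-off** to limit burden. That stands, and nothing here requires them to change.

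**Presentation is not illness onset.** Also true. Hours since presentation cannot recover time since symptoms began, so adjustment would be partial.

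**The link between draw time and severity is conjecture.** It is plausible from the sampling instructions, but neither its strength nor its direction can be taken from the protocol.

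**Conclusion.** The point holds as a mismatch within the protocol. Objective 2, the hypothesis and the rationale place the first sample at presentation or ED admission. The design and sampling sections place it at enrolment, anywhere from 0 to 12 h later. Presentation time is not a named data item. Followed as written, the plan would report samples taken 0 to 12 h after arrival as the response at presentation, and could compare them by outcome without any account of that time.

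The consequence is a risk of confounding in the outcome comparisons, not a demonstrated bias. The fold differences above rest on assumed half-lives and on window extremes.

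It would be wrong to read this as a flaw in the primary objective. If draw timing does not depend on arm, the spread adds noise to the randomised comparison and does not bias it.

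In an exploratory study with no set endpoints, this is a cheap improvement worth making rather than an error that undermines the plan.

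**What to change.** 1. Reconcile Sections 1.1, 1.2 and 2.1.2 with Sections 3, 5.1 and 6.2. State objective 2 and the matching hypothesis as prediction from a sample taken at enrolment, 0 to 12 h after presentation.
2. Name time of presentation in Section 7 and carry it into the sub-study dataset.
3. In Section 9.2, say that change and rate of change use the recorded draw times.
4. In the comparisons by outcome, include hours from presentation to sample as a covariate, or as a sensitivity analysis. For simple accuracy measures such as sensitivity, specificity and ROC curves, a sensitivity analysis in participants sampled early is the easier form. Its cut-off should be fixed before outcomes are examined.
5. Keep the arm comparison on time since enrolment or randomisation. Hours since the start of trial fluid is a post-randomisation clock. It is zero or negative for a baseline sample drawn at or before fluid start, and undefined for anyone who receives none.

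**Cost.** Some rewording, one timestamp, and one or two degrees of freedom in models with few events. If the general sepsis mortality of 22% in Section 1.1 applied here (an assumption), 70 participants would give 0.22 × 70 ≈ 15 deaths, so the time term should be kept simple. Sampling, windows and patient burden stay as they are.

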## 6.3 LONG TERM FOLLOW UP ASSESSMENTS

There is no long term follow up for this study. Participants will be followed up for the ABC sepsis study using routine clinical data at 30 days and 90 days from the medical notes and this data will be shared for the analysis of the MIS-ABC study.

## 6.4 STORAGE AND ANALYSIS OF SAMPLES

At each sampling point during this study, two blood samples will be taken. The first is a 4mL EDTA tube, and the second is a 2.5mL PAXgene tube. From the EDTA tube of blood, we will aliquot one millilitre into cytodelics cell preservation medium for cellular phenotyping (referred to as "cells") and the remaining blood in EDTA tube will be spun down to isolate, which will be stored in aliquots for measuring cytokines.

They will be labelled using pseudonymous study identifiers and stored locally at -80°C until recruitment ends, at which point samples will be shipped to the central laboratory (at the Royal Infirmary of Edinburgh) for analysis.

Consent will be sought for long term storage at the University of Edinburgh for all samples (i.e. PAXgene, cells and plasma), anticipated to be a period of up to 5 years. In the case of the PAXgene tube, funding is not yet secured for the planned sequencing analysis and the samples will be stored until this is possible. Because these tests include genetic analysis, explicit consent will be sought from patients with this in mind. However, the nature of the analysis will be limited to the specific patient presentation and immune response during the time studied.

[figure not shown]
